COVER PAGE

OFFICIAL TITLE OF THE STUDY: PREVENTING DRUG USE AND RISK BEHAVIORS IN ADOLESCENT GIRLS

BRIEF TITLE: SAFE, HEALTHY, ADOLESCENT RELATIONSHIPS AND PEERS (SHARP-TEEN)

NCT NUMBER: NCT02420548

DATE OF DOCUMENT: JANUARY 21, 2019

STUDY PROTOCOL WITH SAP

Brief Summary

Initiation of drug use and participation in sexual-risk behaviors such as having multiple sexual partners, unprotected sexual intercourse, and intercourse with drug users are all too common among female youth with involvement in the child welfare or juvenile justice system. Studies consistently find that these youth have disproportionately higher rates of these problems that, in addition to increasing risk for negative outcomes, have other costly sequelae such as drug addiction, early pregnancy, sexually transmitted infection, HIV contraction, delinquency, and early mortality (e.g., Santelli et al., 2001; Stueve et al., 2005). The goal of this study, which is Research Component 2 within a P50 Center Grant, is to prevent drug use and sexual-risk behaviors in 13–18 year-old girls with early adverse life experiences such as maltreatment ($n = 123$) through the development and evaluation of a preventive intervention.

- 1. To Examine the Effects of the SHARP (Safe, Healthy, Adolescent Relationships and Peers) Intervention on the Developmental trajectories of Drug Use, Sexual-Risk Behaviors, and Delinquency.** We will examine outcomes at intervention termination (approx. 6 months) and a 12-month follow-up using quantitative analysis methods.
- 2. To Examine Mediating Processes Linking the Intervention with Developmental Trajectories of Drug Use, Sexual-Risk Behaviors, and Delinquency.** We will examine two sets of mediators, directly targeted in our intervention: a) improvement in parenting practices, including positive reinforcement, limit setting, and supervision; and b) improvements in the girls' relationships and skills, including peer and partner relations, refusal skills, and goal setting skills. Analyses will focus on whether these two domains partially mediate the effects of the SHARP intervention on the developmental outcomes. Trajectories of drug use, sexual-risk behaviors, and delinquency will be examined separately, and together, in relation to the two proposed sets of mediators.
- 3. To Examine the Influence of Girls' Knowledge and Comfort Around Safe Behaviors on Her Drug Use and Sexual-Risk Behaviors.** Our prior work with girls in the juvenile justice system indicates that they have poor knowledge about safe sex practices and the effects of drugs. Further, a lack of comfort talking about safe sex practices exacerbated the odds contracting a sexually-transmitted infection (Leve et al., 2013). In this Aim, we will examine the role that comfort in discussing safe behaviors and knowledge about safe sex and drug use behaviors has on moderating the intervention effect on trajectories of drug use and sexual-risk behaviors.
- 4. (Exploratory). To Examine Whether Brain Development Moderates the Effect of the Intervention on Developmental trajectories of Drug Use, Sexual-Risk Behaviors, and Delinquency Observed in Aim 1 (above).** We will employ indices of structural and functional brain development as identified in previous studies (Bloch et al. 2013; Dosenbach et al., 2010) in a subset of 25 participants, in order to identify potential salient neurodevelopmental moderators of treatment outcomes.

Study Protocol

Recruitment and retention. The sample will consist of 123 girls between the ages of 13 and 18 and her primary caregiver (123 primary caregivers). Girls will be eligible if they are: (a) female; (b) age 13–18 years at enrollment; (c) reside in Lane County and within 70 miles of the University of Oregon at the time of enrollment; (d) have a current caregiver; (e) and both girl and caregiver are fluent in English. Girls will not be eligible for the study if they (a) are medically fragile; (b) have a significant developmental disability; or (c) have graduated from high school or have a GED. The sample will be recruited in three annual cohorts, with approximately 40 participants each year (~20 intervention, ~20 control/year). A subset of 25 girls in the full sample will be drawn from the final cohort to complete an MRI assessment to address Aim 4.

To recruit the sample, the research team will work collaboratively with the Department of Youth Services in Lane County (DYS) and other community and school-based organizations. For recruitment through community agencies, study staff will provide information about the project and recruitment flyers to liaisons at each agency. Interested families will contact the study recruiter to complete eligibility screening and provide contact information. For recruitment through DHS, a designated study liaison working at these organizations will identify female youth who meet study age eligibility requirements. The liaison will contact eligible families to

provide them with basic information about the study, using the study's recruitment script. Interested families will complete a short screening questionnaire with the liaison. If the family is determined to be eligible, the liaison will collect contact information from the family. During regular meetings, the liaison will provide the study recruiter with the contact information for families who meet study eligibility criteria.

Once the study has received contact information from a potential participant, the recruiter will call the family to provide specific information about the study using the recruitment script. If the girl and her caregiver decide to participate in the study, the recruiter will schedule a time for an in-home visit. At the home visit, both written and verbal explanations of the project will be presented to the caregiver and the youth, along with an opportunity to ask questions about the project. If they agree, caregivers and youth age 18 will sign a study consent form and youth > age 18 will sign a study assent form.

We will use several strategies that we have found facilitate high retention in studies with DYS-involved populations, including adequate compensation for participation, assistance with transportation costs, incentives for updating contact information, and continuity in the staff member responsible for family contact. In addition to tracking placement change information, we have found that we can improve retention for follow-up assessments by sending holiday and birthday cards and study newsletters. Finally, the teen and caregivers will be asked to provide contact information for people who might help locate them and permission to contact those people.

Assessment. Data will be collected through three 2-hour in-person interviews with the teenage girl and her primary caregiver. The interviews will take place either at the participant's home or at the university research center, whichever is most convenient for the participant. The first interview (baseline) will be scheduled immediately after recruitment. The second two interviews will occur 6- and 12- months after the baseline interview, respectively. The caregiver and youth interviews will consist of self-administered questions on a computer and interviewer-administered questions. For the drug use and sexual-risk behavior questions, the interviews and questionnaires have skip patterns, such that youth who report never engaging in any drug use (or sexual-risk behavior) are not asked the follow-up questions about frequency, etc. A short, 10-minute discussion activity involving the teen and her caregiver will be videotaped at the 6-month assessment. Child welfare records pertaining to incidents where the youth participant was reported to be a victim of child maltreatment or neglect will be requested from the State of Oregon. Staff will also collect juvenile court information about the girl from the Department of Youth Services. At the 12-month interview, the teen will provide a urine specimen for a urinalysis (UA). The UA will reveal the presence or absence of a class of drugs in the urine specimen and a second assay will be completed for a subset of youth at the [name] Laboratory at Children's Hospital Los Angeles (CHLA) to measure isoprostane levels (a measure of oxidative stress).

Intervention. Three intervention groups will be conducted per year (7-8 caregivers per parenting group), held on a rolling basis. Girls will be randomly assigned to intervention or control conditions during the baseline assessment home visit, where caregivers will be presented with two sealed, blank envelopes from which to choose. A slip of paper in the envelope will determine study condition (the randomization procedure will target blocks of 20, representing 10 girls in SHARP and 10 corresponding control girls; 10 pieces of paper labeled "SHARP group" and 10 pieces of paper labeled "Usual Services" will be placed in 20 separate unlabeled envelopes).

The intervention (Safe, Healthy, Adolescent Relationships and Peers; SHARP) has two components: a caregiver parenting group that meets weekly for 90-min for 14 weeks, focused on increasing parenting skills, and a Life Coach component where trained and supported skills coaches meet individually with youth weekly for 60 min over the same period to build the girls' social skills and peer/partner relationships skills. Both intervention approaches have been implemented successfully in our previous efficacy trials. We will include all caregiver types (biological, foster, kinship) in parenting groups together. The sessions for the components are based on manualized curricula. Sessions focus on topics such as drug use, HIV-risk behaviors, parental supervision, communication, and peer relations. All intervention staff attend a 5-day experiential training where they are oriented to the theory and perform each of the intervention sessions with other participants playing the role of the caregiver or youth. During the weekly sessions, caregivers and youth are given specific home practice assignments to complete during the week. Intervention sessions are structured to first debrief the home practice, then discuss new content as it relates to the ongoing experiences of the caregivers/youth. Finally, a new home practice is given.

Statistical Analysis Plan

Data will primarily be collected using a computerized program, which allows ready access to the dataset for analysis. The data management and analysis team will clean and check the data on an ongoing basis to ensure quality of the data following the centralized data management protocols. Below we provide descriptions of our procedures for construct development and handling missing data, our hypothesis-testing approach (with specific examples relevant to each Specific Aim), and power analyses.

Construct Development. To avoid inflation of the Type I error rate due to multiple comparisons, we will employ latent construct-building strategies that have standardized criteria for combining various sources of information referring to specific higher-order concepts into latent construct measures (Patterson & Bank, 1986). Multiple indicator composites for core theoretical constructs will be developed where feasible, thus increasing measurement fidelity through stringent requirements of convergent, discriminant, and construct validity (Campbell & Fiske, 1959; Cronbach, 1970). For example, the parenting behavior construct will include youth reports and caregiver reports on parenting behavior. Our criteria for including an indicator in a construct are as follows: the items comprising the indicator must show internal consistency ($\alpha \geq .6$; item-total correlation $\geq .2$), and the scale or indicator created must converge with other indicators designed to assess the construct (the factor loading for the forced one-factor solution $\geq .3$). Some exceptions to these criteria may exist. For example, official arrest records are not necessarily expected to correlate highly with adolescent self-report of delinquent behavior. When disagreements exist between different methods/informants of specific constructs, we will analyze measures separately.

We expect very little missing data over time due to our data collection and data checking procedures, and high retention rates in our previous RCT studies involving similar families. We will first examine the nature of missing data (whether or not the data are missing at random [MAR]) and the pattern of missing data with other predictor variables. Within the context of multiple regressions and multivariate analysis of variance, we will use multiple imputation strategies (Schafer, 1997). For other analyses using latent variable framework (e.g., latent growth model), we will utilize full information maximum likelihood (FIML) estimation, which enables modeling of data sets that have missing data (i.e., the full sample will be used in the analyses without listwise deletion; Curran & Hussong, 2003). FIML is known to produce less biased estimates than listwise deletion, even when the missing at random (MAR) assumption is not strictly met (Arbuckle, 1996).

Analysis Approach. We will rely primarily upon latent growth modeling (LGM) using Mplus 6.12 (Muthén & Muthén, 1998-2010) and the *r* statistical package to take advantage of the longitudinal nature of the study design. The description below presents specific examples of analyses that will be used to test each Aim. Note that demographic characteristics, intervention dosage, caregiver type (foster, biological), and sample (DYS or other) will be included in models as control variables. Early adversity will be included as a covariate. We will use an intent-to-treat approach to all analyses, including all participants in their randomly assigned intervention group, regardless of how many sessions were received.

Aim 1. To Examine the Effect of the SHARP intervention on the Developmental trajectories of Drug Use, HIV-Risk Behaviors, and Delinquency. We hypothesize that girls in the SHARP intervention will show significantly lower levels of drug use, HIV-risk behaviors, and delinquency during follow-ups than the girls in the services-as-usual (SAU) condition. We will test intervention effects using a latent growth modeling (LGM) approach, whereby we will examine group differences in the slope of developmental trajectories of each outcome across T1–T3, controlling for factors described above. As an example, we will examine a two-factor LGM (the intercept and slope) of marijuana use across baseline (T1) through the 12-month follow-up (T3). We hypothesize that the SHARP girls will show significantly lower levels of growth in marijuana use over time than the SAU girls. LGM offers the advantage of testing both the longer-term effects of the SHARP intervention and also to model developmental trajectories. Our assessment includes the same measures at every wave and data are thus particularly well-suited to LGM analyses. Parallel models will be used to examine developmental trajectories of each substance (alcohol, tobacco, marijuana, and all other illicit drugs), HIV-risk behaviors, and delinquency, as well as their co-occurrence.

Aim 2. To Examine Mediating Processes of the Developmental Trajectories of Drug Use, HIV-Risk Behaviors, and Delinquency. This Aim addresses two domains of mediating processes that lead to drug use, HIV-risk behaviors, and delinquency in girls with risk histories. A latent variable model will be used to test the hypothesis that caregivers' parenting practices at T2 mediate the SHARP intervention effect on outcomes at T3. We hypothesize that intervention effects will be significantly related to outcomes (drug use, HIV-risk behaviors, delinquency) at T3 directly and indirectly through parenting behaviors at T2. By comparing the path weights, this test will also allow us to understand the relative strength of immediate and longer-term

intervention effects. All three sets of outcomes (drug use, HIV-risk behaviors, delinquency) will be tested for each of the two hypothesized mediating process separately and simultaneously. In addition, both mediating processes can be examined simultaneously in the model. In the course of these mediational models, we will also examine main effects of the intervention on the mediators.

Aim 3. To Examine the Influence of Girls' Knowledge and Comfort Around Safe Behaviors on Her Drug Use and HIV-Risk Behaviors. We expect moderation of intervention effects by girls' knowledge about safe sex practices, her knowledge of drug use risks and norms, and her comfort talking about safe sex practices. We expect that significant intervention effects on drug use and HIV-risk behaviors will vary depending on girls' level of knowledge and comfort. Lack of knowledge and lack of comfort are expected to potentially reduce intervention effects. The direct effect model can be expanded to test the potential moderating effects of girls' knowledge of safe sex practices and drug use risks and norms.

Aim 4 (exploratory). Indices of brain maturation will be added to the analyses described in Aim 1 to examine the main effect and interaction of brain maturation on intervention outcomes for the three sets of outcomes (drug use, HIV-risk behaviors, delinquency).

Power. In line with the results of our previous work on girls, we expect a medium effect size for the proposed intervention. Power analyses were conducted for two key models to determine whether the proposed sample size ($N = 123$) would be sufficient to detect the hypothesized effects with alpha set at .05 and power of at least .80 (Cohen, 1988). We conducted Monte Carlo simulations in Mplus (Muthén & Muthén, 2002) based on the LGM pictured using 5,000 draws with $\alpha = .05$. We used an estimate of 10% missing data across time in Aim 1. For a medium effect size ($d \approx .45$), all resulting values for the parameter bias ($< 10\%$), standard error bias ($< 10\%$), and coverage ($< .5\%$) satisfied the recommended criteria (Muthén & Muthén, 2002). Furthermore, power to detect intervention effects on the slope factor was .81. We conducted another Monte Carlo analysis to examine power for the mediated model described in Aim 2 including the four control variables listed above. Again, five thousand draws, assuming medium effect sizes (coefficient range = .4–.45) with 10% missing data over time were specified to ensure robustness of the results. All values for the parameter bias, standard error bias, and coverage satisfied the recommended criteria (Muthén & Muthén, 2002) and power to detect direct and indirect intervention effects ranged from .81 to 1.00 in the model. Thus, even though our sample size is modest, current power analyses suggest that it will be sufficient to test all hypothesized models (detect medium effect sizes with power of at least .80).

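### Allocation is balanced in blocks of 20 over three annual cohorts, but no model includes block or cohort, so the arm-effect standard error may be slightly overstated from this source

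*Combined protocol and SAP*

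**What the plan says.** The Intervention paragraph of the Study Protocol describes the allocation: "the randomization procedure will target blocks of 20, representing 10 girls in SHARP and 10 corresponding control girls". The draw takes place at the baseline home visit, where "caregivers will be presented with two sealed, blank envelopes from which to choose".

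Recruitment and retention gives the calendar structure: "The sample will be recruited in three annual cohorts, with approximately 40 participants each year (~20 intervention, ~20 control/year". The cohorts are described as recruitment waves. Nothing says that randomisation is stratified by cohort or restarts with each one.

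The Analysis Approach section of the SAP lists the adjustment terms: "demographic characteristics, intervention dosage, caregiver type (foster, biological), and sample (DYS or other) will be included in models as control variables". It adds: "Early adversity will be included as a covariate". For Aim 1, "we will examine group differences in the slope of developmental trajectories of each outcome across T1–T3, controlling for factors described above". Neither block nor cohort is named in that list, in the descriptions of Aims 1 to 4, or in the Power section.

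**The concern.** When allocation is balanced within a factor that predicts the outcome, differences between levels of that factor largely cancel from the arm contrast. The true sampling error of the contrast then excludes that variance. A model that leaves the factor out still counts the variance as residual, so its standard error is too large from this source. Intervals come out somewhat wide, and a nominal 5% test runs below 5%.

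Here the factor is period of enrolment. Recruitment spans three years and several referral routes, so some drift in the girls enrolled is plausible, but the plan does not measure or discuss it. At stake is a small amount of reported precision and power in a trial of 123 girls whose stated power, .81, sits just above its .80 target.

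**Working it through.** **Inputs from the documents.** N = 123; blocks of 20 at 10:10; three cohorts of about 40; d about .45; alpha .05 (sidedness not stated); 10% missing data; stated power for the slope effect .81.

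**Assumed input.** s, the share of outcome variance lying between recruitment periods after the listed covariates. For Aim 1 this means slope variance. The documents give no value; I use 0, 2%, 5% and 10%.

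**1. The plan's own power figure.** For two equal arms with no covariates, the noncentrality is d × √N / 2.
- N = 123: .45 × √123 / 2 = 2.495. Two-sided power Φ(2.495 − 1.960) = .704; one-sided Φ(2.495 − 1.645) = .802.
- 10% loss, N = 110.7: .45 × √110.7 / 2 = 2.367. Two-sided .658; one-sided .765.

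This closed form does not reproduce .81 with all stated inputs. That does not show .81 to be wrong: it comes from a Monte Carlo growth model whose parameters are not given. I therefore start from .81.

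**2. Standard error and test size.** The ratio of the standard error with period omitted to that with it included is 1/√(1 − s). The two-sided size with period omitted is 2 × [1 − Φ(1.96/√(1 − s))].

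**3. Power after adjustment.** Power of .81 corresponds to a noncentrality of 1.960 + 0.878 = 2.838. Adjusting multiplies it by 1/√(1 − s).

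| s (assumed) | SE ratio | Size, omitted | Noncentrality, adjusted | Power, adjusted |
|---|---|---|---|---|
| 0 | 1.000 | .050 | 2.838 | .810 |
| .02 | 1.010 | .048 | 2.867 | .818 |
| .05 | 1.026 | .044 | 2.912 | .829 |
| .10 | 1.054 | .039 | 2.991 | .849 |

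A noncentral t calculation charging 2 degrees of freedom for cohort, or 5 to 6 for block, gives the same powers to within .001.

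The gain over .81 in the last column is an upper figure. With period omitted, the estimate also varies less than its standard error implies, so the actual power of the unadjusted test is Φ(0.878/√(1 − s)) = .812, .816 and .823 for the three non-zero shares. Measured that way, the gain is about .005, .013 and .026.

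**4. Simulation check.** Permuted blocks of 20 were simulated with N = 123, a single outcome and 4,000 runs per setting.
- Share .05: mean model standard error .1794 with block omitted against .1761 with it included (ratio 1.019); type I error .046 against .051.
- Share .10: .1789 against .1715 (ratio 1.043); type I error .040 against .049.
- True SD of the estimate at share .10: .1722 against .1721.

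The Monte Carlo error on a rate near .05 is √(.05 × .95/4000) = .003. The direction agrees with step 2, and the size is a little smaller. The estimate itself is equally precise either way; only its reported standard error changes.

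**5. The opposing error.** SHARP caregivers meet in groups of 7 to 8; controls have no such groups. With m per group and intraclass correlation ICC in one arm only, the true standard error is √{[(1 + (m − 1) × ICC) + 1]/2} times what a model ignoring the groups reports. For m = 7 and an assumed ICC of .05 this is √(2.30/2) = 1.072; for m = 8 and ICC .10 it is √(2.70/2) = 1.162. In simulation with groups of 7 and a block share of .02, type I error was about .06 (ICC .05) and .09 (ICC .10), and adding block did not correct it.

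**The case against.** The strongest reply is that these are blocks of consecutive enrolment, not a prognostic stratum, and that s may be close to zero. Recruitment source, demographic characteristics, caregiver type and early adversity are already in the models and would absorb part of any drift in referral mix. In Aim 1 a stable difference in level between periods goes to the intercept, so only drift in the slope matters. All of this stands, and it is why the point is conditional. It has less force for Aim 2, which models parenting at T2 and outcomes at T3, where level differences enter directly.

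Block terms are also not free. 123 girls make six full blocks (120) and a remainder of 3. Seven blocks need six indicators, which on two growth factors is 12 extra parameters per outcome. This stands too, and it favours cohort as the main adjustment.

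Three stronger readings are tempting, and the documents do not support them.
- *The arm standard errors are too wide and the p-values conservative.* This needs a non-zero s, which is not given, and it ignores the parenting groups, whose effect is opposite and could be larger. In addition, intervention dosage is tied to arm and sits in the same models, so the simple ratio describes the planned arm coefficient only approximately.
- *Precision is thrown away at no cost.* Blocking has already secured the precision of the estimate. Adjustment corrects the reported standard error and recovers a little power, at the price of extra parameters.
- *Randomisation is blocked within annual cohorts.* Two blocks of 20 fit a cohort of about 40, but the plan does not link them, and it calls the blocks a target.

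**Conclusion.** The point holds as a minor one. The plan restricts its randomisation and recruits in annual waves, and its analysis reflects neither. If recruitment period predicts the outcome beyond the listed covariates, the arm standard error is overstated from this source by about 1.0%, 2.6% or 5.4% at assumed shares of 2%, 5% or 10%, and not at all at 0. Starting from .81, adjusted power is about .82, .83 or .85. These figures rest on the assumed share, on near-exact 10:10 balance within periods, and on a simple two-arm contrast standing in for the growth-model slope. Whether reported standard errors are too wide or too narrow overall cannot be settled from the documents.

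**What to change.** - In the SAP, add annual cohort (two indicators) as a predictor of intercept and slope in each Aim 1 model, and of the mediator and outcome in each Aim 2 model.
- Record the block number with each assignment; the protocol does not mention doing so.
- Specify a sensitivity analysis that uses block in place of cohort, with the final partial block of about 3 girls merged into the preceding one. That leaves six blocks and five indicators.
- Handle clustering by parenting group in the SHARP arm separately; a cohort or block term does not address it.

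The cost is SAP wording, one recorded field, and 2 indicators × 2 growth factors = 4 extra parameters per Aim 1 model with N = 123. If cohort does not predict outcome there is no gain, and the power loss is negligible (about .810 either way).

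### The Aim 1 test of arm on slope adjusts for intervention dosage, which arises after randomisation, so unless dosage is centred within arm the arm coefficient is not the effect of assignment

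*Combined protocol and SAP*

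**What the plan says.** The Analysis Approach section of the SAP lists the adjustment variables once for all models: demographic characteristics and then "intervention dosage, caregiver type (foster, biological), and sample (DYS or other) will be included in models as control variables". Early adversity is added as a further covariate. The same paragraph promises intent-to-treat analysis, "including all participants in their randomly assigned intervention group, regardless of how many sessions were received".

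Aim 1 brings the list into the main test, which examines "group differences in the slope of developmental trajectories of each outcome across T1–T3, controlling for factors described above". Aim 2 adds that "we will also examine main effects of the intervention on the mediators". Aim 3 builds on Aim 1: "The direct effect model can be expanded to test the potential moderating effects". Aim 4 adds brain-maturation indices to the Aim 1 analyses.

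The timing is in the Study Protocol, under Intervention: "Girls will be randomly assigned to intervention or control conditions during the baseline assessment home visit". SHARP then consists of "a caregiver parenting group that meets weekly for 90-min for 14 weeks" and a Life Coach component in which "skills coaches meet individually with youth weekly for 60 min over the same period".

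The documents do not say which component counts as dosage, how the two combine, what value usual-services girls receive, or whether dosage is centred. No model without dosage is planned.

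**The concern.** Dosage is a consequence of assignment and of how each family behaves afterwards. Adjusting the arm contrast for it replaces the question Aim 1 asks (does being offered SHARP lower growth in drug use, HIV-risk behaviour and delinquency?) with a contrast at a fixed number of sessions. If usual-services girls score zero, that number is zero.

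The result then depends on how attendance relates to outcome. A programme that works through its sessions could look ineffective. A programme with no effect could look helpful or harmful if families who attend more differ in prognosis. In Aim 2 the intervention-to-mediator path fails in the same way and takes the indirect effect with it.

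**Working it through.** **The plan's own figure.** The Power section reports .81 for the slope effect with N = 123, d about .45, alpha .05 and 10% missing data. A plain two-group comparison has SE = sqrt(1/62 + 1/61) = 0.180, so 0.45/0.180 = 2.50 and two-sided power is .70 (.66 if 10% of girls are lost; one-sided .80 and .77). The growth variances and sidedness behind .81 are not given, so it cannot be reproduced. It is not disputed here, because nothing shows that dosage was in that simulation.

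**What the arm coefficient becomes.** Let A be arm and D sessions attended, with D = 0 in usual services (an inference). In Y = a + bA + cD, the coefficient c is estimated only from variation within SHARP, and

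b = (mean Y in SHARP - mean Y in usual services) - c × (mean D in SHARP).

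- Benefit proportional to sessions: the arm difference equals c × mean D, so b = 0.
- Constant effect and within-SHARP correlation r between attendance and outcome (outcome SD 1): c = r/SD(D), so b = effect - r × mean(D)/SD(D).
- Grand-mean centring of D changes the intercept and leaves b alone. Centring within arm makes D uncorrelated with A, and b is again the assignment effect.
- The variance inflation for A is about 1 + 0.5 × mean(D)²/SD(D)².

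**Numbers.** Attendance is assumed. The runs used 10,000 replicates per scenario, 62 and 61 girls, residual SD 1 and a true effect of -0.45 except in the last row.

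| Mean (SD) sessions of 14 | 7.0 (4.3) | 8.7 (4.2) | 9.7 (3.5) | 10.8 (2.6) |
|---|---|---|---|---|
| mean/SD | 1.63 | 2.07 | 2.77 | 4.15 |
| b by formula, r = -0.2: -0.45 + 0.2 × mean/SD | -0.12 | -0.04 | +0.10 | +0.38 |
| b simulated, r = -0.2 | -0.12 | -0.04 | +0.11 | +0.39 |
| Power, constant effect, r = 0 (about 70% without dosage) | 37% | 28% | 20% | 12% |
| False positives by formula, no effect, r = ±0.2 | 22% | 26% | 29% | 32% |

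The false-positive row takes a normal estimate with mean 0.2 × mean/SD and SE 0.180 × sqrt(variance inflation). For the first column, 0.2 × 1.63 = 0.33 and 0.180 × sqrt(2.3) = 0.27.

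Other simulated results over the same four scenarios:

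- Variance inflation for arm is 2.4 to 9.8, and the SE rises from 0.18 to 0.28-0.56.
- Proportional benefit: the estimate goes from -0.45 to about 0.00, and rejection from 67-70% to 5-6%.
- Constant effect, r = +0.2: the estimate is -0.77 to -1.27.
- No effect: false positives are 9-11% at r = 0.1 and 21-32% at r = 0.2 (either sign), against 4-6% without dosage.
- Centring within arm gives about -0.45 with SE 0.18.

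**Other attendance assumptions.** With attended shares of mean/SD .6/.3, .7/.25 and .8/.15, the pattern is the same. Power under a constant effect falls to 9-27%. If half the effect runs through dosage, the estimate is about -0.20 to -0.23.

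**Growth-model check.** A three-wave random-intercept and random-slope model was fitted by maximum likelihood with 10% missing at T2 and at T3. It used the lowest and highest attendance scenarios, 432 replicates each, and variances set so that power without dosage is about .8. The SE grows by factors of 1.5 and 3.1. Power under a constant effect falls from 82% to 48% and 16%, and under proportional benefit from 79-82% to 5-6%. False positives are 15-20% when attendance correlates 0.2 with the latent slope.

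**Aims 2 and 3.** In an Aim 2 stand-in with proportional benefit, arm to mediator 0.45 and mediator to outcome -0.4, the arm-to-mediator path goes from 0.45 to 0.00. The indirect effect goes from 0.45 × -0.4 = -0.18 to 0.00, and joint significance from 68-69% to 4-5%. In an Aim 3 stand-in the arm term fails as in Aim 1, but the arm-by-moderator term moves by at most 0.08 (SE 0.18 to 0.19). Aim 4 was not simulated.

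**The case against.** The strongest reply is that the plan commits to intent-to-treat and that the model form is inferred. The intent-to-treat sentence settles who is analysed and in which arm. It takes nothing out of the covariate list, so the two sentences conflict.

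On model form, the SAP speaks of group differences in slope and does not write out the equation. A contrast of model-implied slope means, evaluated at the mean SHARP dosage, would recover the assignment effect just as centring within arm does. That is correct, but the plan specifies neither. A two-group growth model that compared intercepts without centring would still refer to zero sessions.

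Three further points stand in part:

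- If the effect is constant and attendance is unrelated to prognosis within SHARP, the adjusted estimate is unbiased and only power is lost.
- Every magnitude rests on assumed attendance and on zero dosage in usual services. Scoring dosage differently in that arm would change the figures, but the adjustment would still be for a post-randomisation variable.
- The harm to the Aim 3 interaction is small, and Aim 4 is exploratory with 25 girls. The case is strongest for Aim 1 and for the Aim 2 intervention-to-mediator path.

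The Aim 2 power of .81 to 1.00 is no defence. That simulation is said to include four control variables. The Analysis Approach lists exactly four (demographics, dosage, caregiver type, sample), so dosage was probably among them. How it was generated, and in particular whether it was tied to arm, is not stated.

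**Conclusion.** The concern holds and should be fixed before analysis. By explicit cross-reference, the Aim 1 test adjusts for a variable that arises after randomisation. The algebra does not depend on the attendance pattern: with dosage zero in usual services and not centred within arm, the arm coefficient is the contrast at zero sessions. It matches the assignment effect only when outcome is unrelated to dosage within SHARP, and then with a much larger standard error.

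The size does depend on attendance. Over the assumed range, a real effect of -0.45 SD can be estimated anywhere from about -1.27 to +0.39, and false positives can reach about 32%. These figures are illustrations from stand-in models without the other covariates. None is the sponsor's Mplus model.

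**What to change.** - Delete intervention dosage from the control variables in the Aim 1 models, in the Aim 3 and 4 models that extend them, and in the Aim 2 tests of the intervention's effects on the mediators.
- Keep demographics, caregiver type, sample source and early adversity, each stated as measured at baseline. For caregiver type this is a clarification: the Recruitment and retention section tracks placement changes, so its value could change after randomisation.
- In the Aim 2 mediation model, do not adjust the total effect or the intervention-to-mediator effect for dosage. If dosage is thought to confound mediator and outcome, use a separately labelled sensitivity analysis. In the stand-in where attendance also affected T3 outcome directly, the mediator-to-outcome path was -0.43 to -0.41 without dosage and -0.40 with it, so little is lost.
- Define dosage: which component, how the two combine, and the value in usual services. Report any within-SHARP dose-response analysis, or a complier-average analysis with randomisation as instrument, separately and labelled as not intent-to-treat.
- Repeat the Aim 2 power simulation if dosage was one of its four control variables, and any other simulation that included it.

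The cost is a short SAP wording change, plus a repeated simulation only where dosage was included. No new data are needed.
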